Immunogenicity of PPSV-23 after PCV-13 Vaccination in Adult Asthmatic Patients

NCT03260790

6/7/2018

IRB Minimal Risk Protocol Template

Note: If this study establishes a human specimen repository (biobank) for research purposes, do not use this template. Use the Mayo Clinic Human Specimen Repository Protocol Template found on the IRB home page under Forms and Procedures at <http://intranet.mayo.edu/charlie/irb/>

First-time Use: Use this template to describe your study for a new IRB submission.

1. Complete the questions that apply to your study.
2. Save an electronic copy of this protocol for future revisions.
3. When completing your IRBe application, you will be asked to upload this document to the protocol section.

Modification: To modify this document after your study has been approved:

1. Open your study in IRBe. Click on the study 'Documents' tab and select the most recent version of the protocol. Save it to your files.
2. Open the saved document and activate "Track Changes".
3. Revise the protocol template to reflect the modification points , save the template to your files
4. Create an IRBe Modification for the study and upload the revised protocol template.

General Study Information

Principal Investigator: [name]

Study Title: **Immunogenicity of PPSV-23 after PCV-13 Vaccination in Adult Asthmatic Patients**

Protocol version number and date: Protocol version number 3. 06/07/2018

Research Question and Aims

Hypothesis:

- 1) Priming with PCV13 will result in increased immunogenicity of PPSV23 in asthmatic subjects
- 2) Priming with PCV13 will result in durable immunogenicity of the PPSV23 in asthmatic subjects

Aims, purpose, or objectives:

Aim 1 will compare the safety and immunogenicity of PPSV23 and PCV13 vaccines in asthmatic subjects. The vaccine response of randomized asthmatic patients to either PPSV 23 alone (Group A) or PCV13 with PPSV23 given 8 weeks later (Group B) will be compared. Immunogenic response will be assessed and compared between groups at 8 and 16 weeks after vaccination.

Aim 2 will compare the changing of immunologic response in the two arms over the subsequent 8 weeks' time frame in both Group A and Group B.

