
Study Design and Methods**Methods: Describe, in detail, the research activities that will be conducted under this protocol:**

Subjects: 50 adult patients diagnosed with asthma will be recruited from patients seen in the Division of Allergic Diseases and from Primary Care; volunteers will also be solicited with flyers and electronic announcements. The patients recruited will be between 19 and 64 years of age. Exclusion criteria include

research exemption requested, history of PCV-13 vaccination, age \leq 19 or \geq 64, history of cochlear implant, CSF leak, CHF, DM, CKD, HIV, CVID as well as patients who have received the PPSV23 vaccine in the last 5 years. Women who are pregnant will also be excluded from the study. They will be contacted at the end of their visit to discuss enrollment in the study by the research coordinator.

Protocol: The patients will then be randomized into either Group A (standard of care) or Group B (experimental group). At the week 0 time point, the patients will receive either PPSV23 vaccine (Group A) or PCV13 (Group B) and undergo a blood draw of 5mL for assessment of pre-vaccination serotype titers. Group A will undergo a 5mL draw for assessment of titers at week 8, 16, and 24 following vaccination. Group B will undergo vaccination with PPSV23 at Week 8 with 5mL draw for pneumococcal serotype titers as well as a blood draw at Week 16 and Week 24. Immunogenicity will be analyzed by assessing for serotype-specific IgG as well as total IgG binding. Samples will be run at Mayo Rochester, and samples will additionally be shipped to a third party, The Binding Site, for further antipneumococcal binding assays. The samples will be identified to The Binding Site only by their study-specific identification number (i.e. A01, B01 etc). The Binding Site will not receive any patient identifying information.

Resources: *Describe the available resources to conduct the research (personnel, time, facilities, mentor commitment, etc.):*

This study is being conducted by [name], [name], [name], and [name]. [name], PGY4, has 9 months of dedicated research time.

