(1a) This is a multisite study involving Mayo Clinic and non Mayo Clinic sites. *When checked, describe in detail the research procedures or activities that will be conducted by Mayo Clinic study staff.*

(1b) Mayo Clinic study staff will be engaged in research activity at a non Mayo Clinic site. *When checked, provide a detailed description of the activity that will be conducted by Mayo Clinic study staff.*

Subject Information

Target accrual is the proposed total number of subjects to be included in this study at Mayo Clinic. A "Subject" may include medical records, images, or specimens generated at Mayo Clinic and/or received from external sources.

Target accrual: 50

Subject population (children, adults, groups): Adults

Inclusion Criteria: Ages 19 to 64 with diagnosis of asthma

Exclusion Criteria: Exclusion criteria include research exemption requested, history of PCV-13 vaccination, age $<$ 19 or $>$ 65, history of cochlear implant, CSF leak, CHF, DM, CKD, HIV, CVID as well as patients

who have received the PPSV23 vaccine in the last 5 years. Women who are pregnant will also be excluded from the study by performing 2 point of care urine pregnancy tests (prior to vaccinations)

Research Activity

Check all that apply and complete the appropriate sections as instructed.

1. **Drug & Device:** Drugs for which an investigational new drug application is not required. Device for which (i) an investigational device exemption application is not required; or the medical device is cleared/approved for marketing and being used in accordance with its cleared/approved labeling. (Specify in the Methods section)
2. **Blood:** Collection of blood samples by finger stick, heel stick, ear stick, or venipuncture.
3. **Biological specimens other than blood:** Prospective collection of human biological specimens by noninvasive means that may include: urine, sweat, saliva, buccal scraping, oral/anal/vaginal swab, sputum, hair and nail clippings, etc.
4. **Tests & Procedures:** Collection of data through noninvasive tests and procedures routinely employed in clinical practice that may include: MRI, surface EEG, echo, ultrasound, moderate exercise, muscular strength & flexibility testing, biometrics, cognition testing, eye exam, etc. (Specify in the Methods section)
5. **Data** (medical record, images, or specimens): Research involving use of existing and/or prospectively collected data.

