Subject ID, subject code or any other person-specific unique identifying number, characteristic or code that can link the subject to their medical data	x	x
Dates: All elements of dates [month, day, and year] directly related to an individual, their birth date, date of death, date of diagnosis, etc.	x	
Note: Recording a year only is not a unique identifier.		
Social Security number		
Medical device identifiers and serial numbers		
Biometric identifiers, including finger and voice prints, full face photographic images and any comparable images		
Web Universal Resource Locators (URLs), Internet Protocol (IP) address numbers, email address		
Street address, city, county, precinct, zip code, and their equivalent geocodes		
Phone or fax numbers		
Account, member, certificate or professional license numbers, health beneficiary numbers		
Vehicle identifiers and serial numbers, including license plate numbers		
Check 'None' when none of the identifiers listed above will be recorded, maintained, or shared during the conduct of this study. (exempt category 4)	 None	 None

Data Analysis

Power analyses and study endpoints are not required for minimal risk research, pilot or feasibility studies.

No statistical information. *If checked, please explain:*

Data Analysis:

For each of the 23 serotypes, exact, unconditional, 2-sided 95% confidence intervals (CIs) on the single proportions will be calculated using the F distribution. The 95% CIs for the difference in proportions ([PCV-13+PPSV23] – [PPSV23]) will be computed using the non-inferiority procedure of Chan and Zhang, using the standardized test statistic and $\gamma=0.000001$. Non-inferiority is declared if the lower CI for the difference is >-0.10 . Similar procedures will be used for the evaluation of antibody concentrations after 12 months.

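### Aim 1 promises a comparison of vaccine safety, but the documents describe no adverse-event collection and no safety analysis, so the safety component of Aim 1 cannot be answered as planned

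*Combined protocol and SAP*

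**What the plan says.** Under Research Question and Aims, the first sentence of Aim 1 reads "Aim 1 will compare the safety and immunogenicity of PPSV23 and PCV13 vaccines in asthmatic subjects". The same paragraph then makes the aim operational for immune response only: "Immunogenic response will be assessed and compared between groups at 8 and 16 weeks after vaccination". Both hypotheses and Aim 2 also concern immune response only.

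Under Study Design and Methods, each group's schedule consists of vaccinations and blood draws:

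- Week 0, both groups: the assigned vaccine, and subjects "undergo a blood draw of 5mL for assessment of pre-vaccination serotype titers".
- Group A afterwards: "Group A will undergo a 5mL draw for assessment of titers at week 8, 16, and 24 following vaccination".
- Group B afterwards: "Group B will undergo vaccination with PPSV23 at Week 8 with 5mL draw for pneumococcal serotype titers", then draws at Weeks 16 and 24.

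The outcome is stated as "Immunogenicity will be analyzed by assessing for serotype-specific IgG as well as total IgG binding".

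The one safety-related procedure is in the exclusion criteria under Subject Information: "Women who are pregnant will also be excluded from the study by performing 2 point of care urine pregnancy tests". The Data Analysis section opens with "For each of the 23 serotypes, exact, unconditional, 2-sided 95% confidence intervals (CIs) on the single proportions will be calculated using the F distribution" and continues with differences in proportions, geometric means, geometric mean ratios and fold rises. All of these are antibody measures.

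**The concern.** A stated aim of a randomized comparison has neither a data source nor an analysis. This is more than a missing definition. An undefined antibody endpoint can still be defined later from stored titers, but adverse events that nobody asked about during 24 weeks of follow-up cannot be reliably recovered.

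The design also makes informal safety data hard to read. Group B has two injections and Group A one, so a raw count of spontaneous reports mixes the effect of the vaccine with the number of exposures. No blinding or placebo is described, so subjects and staff probably know the allocation, and unprompted reporting could then differ between arms. A lack of reports could be mistaken for comparable safety, with no systematic ascertainment behind it.

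**Working it through.** **Step 1: trace the aim through the documents.** There is no stated safety rate, power or sample-size derivation to reproduce, so the main check sets the sections side by side.

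| Place | Immunogenicity | Safety |
|---|---|---|
| Hypotheses 1 and 2 | Yes | None |
| Aim 1, first sentence | Yes | Named |
| Rest of Aim 1, and Aim 2 | Yes | None |
| Methods, Week 0 | Titers | None |
| Methods, Weeks 8, 16 and 24 | Titers | None |
| Methods, outcome | Serotype-specific and total IgG | None |
| Exclusion criteria | n/a | Pregnancy test, an eligibility screen |
| Data Analysis, main | Proportions by serotype | None |
| Data Analysis, secondary | Geometric means, ratios, fold rises | None |

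Safety is named as something to compare in one sentence only. No solicited or unsolicited event collection, diary, record of asthma worsening, serious-event follow-up, safety population or adverse-event table is described.

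**Step 2: compare exposure by interval** (from the Methods schedule).

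- Weeks 0 to 8: Group A has had one PPSV23 injection and Group B one PCV13 injection. This is a like-for-like count, and it is the contrast that Aim 1 names.
- From Week 8: Group B has had two injections and Group A still one.

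Any safety summary therefore has to be split by injection or interval.

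**Step 3: what could the data show if collected?** Target accrual is 50 (Subject Information). The allocation ratio is not stated, so I assume 25 per arm.

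- Upper limit with zero events, two-sided 95%: 1 − 0.025^(1/25) = 0.137, or 13.7%. For an uneven split of 20 and 30, the limits would be 1 − 0.025^(1/20) = 16.8% and 1 − 0.025^(1/30) = 11.6%.
- Chance of at least one event in an arm of 25, 1 − (1 − r)^25: 22% at r = 1%, 40% at 2%, 72% at 5%, 93% at 10%.
- Power to detect a difference between arms (two-sided 0.05, normal approximation with pooled variance under the null), where p̄ is the mean of the two rates: Φ{[|p2 − p1|√n − 1.96√(2p̄(1 − p̄))] / √(p1(1 − p1) + p2(1 − p2))}. For 10% against 20% with n = 25, this is Φ[(0.500 − 0.990)/0.500] = Φ(−0.98) = 16%. The same formula gives 42% for 10% against 30%, and 81% for 10% against 45%.

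The event rates are illustrative; the documents give none. The figures show that collected data would describe common reactions but would not support a formal comparison unless the arms differed greatly.

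**The case against.** The best case against is that this is one word in one sentence. The title, both hypotheses, Aim 2, the background and the rest of Aim 1 concern immune response, and no decision rule depends on safety. The form is a minimal-risk template that requires neither power calculations nor endpoints. Checkbox marks were lost when the PDF was read and consent pages were removed, so medical-record review or institutional event reporting may exist out of sight. Questions at eight-week intervals would recall mild reactions poorly, and 50 subjects could not support a formal comparison anyway.

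Much of this limits what can be claimed. A reader might infer that half of Aim 1 is lost, that none of the 50 subjects will have safety data, that the trial is open-label, or that the team intends to claim comparable safety. The documents support none of these as fact:

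- Immunogenicity is the substance of the aim.
- Silence in documents with lost checkboxes shows only that no collection is described.
- Lack of blinding is inferred from the absence of any mention of blinding or placebo and from the differing injection schedules.
- No passage plans a claim of equal safety.

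The core survives. The Methods prompt asks for a detailed account of the research activities, and the answer contains no safety capture. Unseen reporting would still not be a planned comparison between arms. The template's waiver explains a thin analysis section, but it does not supply data for an aim the team chose to state. If safety really is incidental, the right response is to remove it from the aim.

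**Conclusion.** The point holds in this form: Aim 1 promises a safety comparison, the documents describe neither safety data collection nor safety analysis, and the safety component cannot be answered if the plan is followed as written. The immunogenicity aims and their planned estimates are unaffected. It should be corrected, but it does not undermine the trial's main purpose.

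The mismatch rests on the text alone and needs no numerical assumption. The 13.7% limit and the detection and power figures depend on 25 per arm and on illustrative event rates. They set expectations for what could be learned and do not measure the flaw itself.

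**What to change.** Choose one of two routes.

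**Collect and describe.**

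- Record a pre-vaccination baseline at Week 0. That visit cannot yield post-vaccination events.
- At the existing Week 8, 16 and 24 visits, ask every subject in both groups the same short questions on injection-site and systemic reactions, asthma worsening and serious events since the last visit.
- Preferably add a simple take-home record for the days after each injection, to limit recall error.
- In the Data Analysis section, plan one table of counts with exact 95% intervals, by arm and by injection. Use Weeks 0 to 8 as the one-injection-each comparison of PPSV23 with PCV13. For later intervals, state that Group B has had two injections and Group A one.
- Label the results descriptive.

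**Or narrow the aim.** If these data will not be collected, delete safety from Aim 1 and draw no safety conclusion.

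The first route costs a protocol modification, a short form (with the take-home record if used) and one extra table, with no extra visits. Mild reactions will still be under-captured, and reporting by subjects who probably know their arm limits interpretation. The second route costs a one-word edit through the same modification process.

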**Background (Include relevant experience, gaps in current knowledge, preliminary data, etc.):**

S pneumoniae is the leading bacterial cause of pneumonia and invasive pneumococcal disease and is a significant cause of morbidity and mortality in the United States with \$16.2 billion dollars spent in healthcare-related costs in 2013¹. The CDC currently recommends the polysaccharide PPSV23 vaccination (Pneumovax®) in all adults over the age of 65 as well as in individuals with chronic lung disease.

Pneumococcal conjugate vaccine PCV13 (Prevnar ®), initially developed for use in children, is currently recommended for immunocompromised adults and individuals with cerebrospinal fluid leaks and cochlear implants. There is some debate as to whether PPSV23 leads to a decrease in prevalence of disease caused by *S. pneumoniae*, indeed, a 2009 meta-analysis funded by the WHO found that the evidence supporting its use was poor.² In 2014, vaccination guidelines changed to support the use of PCV13 in patients over the age of 65 after it was found to be efficacious in preventing community acquired pneumonia and invasive pneumococcal disease in the elderly population.³ The PCV13 vaccine contains polysaccharide antigens conjugated with a protein carrier whereas the PPSV23 contains polysaccharide antigens alone. It is proposed that the conjugate vaccine induces immunity via a T-cell dependent process. Given that patients with asthma are disproportionately affected by pneumococcal disease, it is imperative that the vaccination strategy for pneumonia be as immunogenic and efficacious at eliciting a robust immune response as possible.

To address this, we propose to compare the response to PPSV23 with a novel schedule of PCV13 followed by PPSV23 given eight weeks later in adult patients with asthma. We will assess the immune system at 8 weeks and 16 weeks post vaccination. Given that the PCV13 vaccine elicits immunity via a T-cell dependent mechanism, we hypothesize that giving PCV13 in conjunction with PPSV23 will lead to an enhanced immune response in asthmatic patients.

References

1. American Lung Association. Trends in Pneumonia and Influenza Morbidity and Mortality. November 2015.

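### Aim 1 does not say which vaccination its 8 and 16 weeks count from; counted from the first dose, those contrasts compare vaccines or schedules and do not test the priming hypotheses

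*Combined protocol and SAP*

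**What the plan says.** The first hypothesis is that "Priming with PCV13 will result in increased immunogenicity of PPSV23 in asthmatic subjects"; the second concerns how durable that response is. Aim 1 opens broadly: "Aim 1 will compare the safety and immunogenicity of PPSV23 and PCV13 vaccines in asthmatic subjects". It then sets PPSV23 alone against the PCV13-then-PPSV23 sequence, and gives the timing: "Immunogenic response will be assessed and compared between groups at 8 and 16 weeks after vaccination". The Background repeats the timing, again with no dose named: "We will assess the immune system at 8 weeks and 16 weeks post vaccination". Aim 2 follows on: "Aim 2 will compare the changing of immunologic response in the two arms over the subsequent 8 weeks".

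Study Design and Methods gives the visits. Group A receives PPSV23 and Group B PCV13 at week 0, each with a baseline draw. After that, "Group A will undergo a 5mL draw for assessment of titers at week 8, 16, and 24 following vaccination", while "Group B will undergo vaccination with PPSV23 at Week 8 with 5mL draw for pneumococcal serotype titers", with further Group B draws at weeks 16 and 24. Both arms are therefore sampled at study weeks 0, 8, 16 and 24.

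Data Analysis names no 8- or 16-week time point. Its only times are at 12 months: once for antibody concentrations analysed by procedures similar to those for the proportions, and once for the fold rise, which is counted from PPSV23 in each arm. It sets non-inferiority margins of -0.10 for the difference in proportions and 0.5 for the geometric mean ratio (GMR).

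**The concern.** Group A has one vaccination and Group B has two, eight weeks apart, so a time counted from vaccination is not defined for a between-arm comparison until the dose is named. The hypotheses ask whether PCV13 beforehand changes the response to PPSV23. That calls for the arms to be compared at the same time after PPSV23.

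If the analyst counts from the first dose, the first contrast involves no PPSV23 response in Group B. The second compares the arms at different distances from PPSV23. Waning in Group A over its extra eight weeks could then be read as a benefit of priming. The same draws support either analysis, so while the anchor is open the choice can be made after the results are seen.

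**Working it through.** **Inputs.** PPSV23 is given at study week 0 in A and week 8 in B; draws are at weeks 0, 8, 16 and 24 (Study Design and Methods). The margins come from Data Analysis. The plan states no figure on this point, so there is none to reproduce.

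**Step 1: counting from the first dose.** Weeks since PPSV23 = study week minus PPSV23 week.

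| Study week | A | B | Gap |
|---|---|---|---|
| 8 | 8 - 0 = 8 | 8 - 8 = 0 | 8 |
| 16 | 16 - 0 = 16 | 16 - 8 = 8 | 8 |
| 24 | 24 - 0 = 24 | 24 - 8 = 16 | 8 |

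At week 8, B has responded to PCV13 only, provided the draw precedes the PPSV23 dose given at that visit; the protocol does not state the order. On this count Aim 1's two times are study weeks 8 and 16. Week 24 enters only through Aim 2.

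**Step 2: counting from PPSV23.**

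| Weeks after PPSV23 | A draw | B draw | Both scheduled? |
|---|---|---|---|
| 8 | week 8 | week 16 | yes |
| 16 | week 16 | week 24 | yes |
| 24 | week 24 | week 32 | no (B) |

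Both Aim 1 times can be matched from draws already planned.

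**Step 3: which count Aim 2 fits.**
- First dose, window opening at week 16: study weeks 16 to 24 in both arms. This fits and uses every draw, but covers 16 to 24 weeks after PPSV23 in A and 8 to 16 in B.
- PPSV23, window opening at 16 weeks: B would need week 32, which is not scheduled.
- PPSV23, window opening at 8 weeks: A weeks 8 to 16, B weeks 16 to 24. This fits, but leaves A's week-24 draw unused.

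The schedule therefore does not settle the anchor.

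**Step 4: 12-month time points.** Taking 12 months as 52 weeks, 12 months after PPSV23 is study week 52 in A and 52 + 8 = 60 in B. The last draw is week 24.

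**Step 5: illustrative size at study week 16.** The documents give no waning rate, SD, allocation ratio or responder definition. Assume exponential waning with half-life h weeks and no priming effect. The apparent B/A ratio is then 2^(8/h). Assume also 25 per arm and a ln SD of 1.0, so SE = sqrt(2/25) = 0.283. The last column is the chance that the lower 95% limit exceeds 0.5 when the true GMR at equal time since PPSV23 is 0.5 (noncentral t, 48 df).

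| h (weeks) | Apparent ratio, no priming effect | Non-inferiority declared at true GMR 0.5 |
|---|---|---|
| no waning | 1.00 | 2.5% |
| 104 | 1.05 | 3.8% |
| 52 | 1.11 | 5.6% |
| 26 | 1.24 | 11% |
| 16 | 1.41 | 22% |

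At h = 16 the last figure is 32% with ln SD 0.8 and 17% with ln SD 1.2.

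For proportions, assume a fixed cut-off and 70% of each arm above it 8 weeks after PPSV23. The apparent difference with no priming effect then runs from 0 points (no waning) to 12.9 (h = 16, where A's 70.0% falls to 57.1%). A fall that crosses no cut-off changes no proportion, so this depends on a responder definition the plan does not give.

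**Step 6: Aim 2 over study weeks 16 to 24.** Under exponential waning both arms change by 2^(-8/h), so there is no bias. If titre instead falls as t^-0.3, A changes by (24/16)^-0.3 = 0.885 and B by (16/8)^-0.3 = 0.812. The ratio is 0.812/0.885 = 0.917, against priming. The direction is not known in advance.

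**The case against.** The strongest reply is that the plan already points to PPSV23. The title and both hypotheses concern the PPSV23 response, the only dose-specific anchor in Data Analysis is PPSV23, and the draws fall 8 and 16 weeks after PPSV23 in both arms. The week-32 difficulty disappears if Aim 2's window opens at 8 weeks. All of this stands and makes PPSV23 a natural choice. It does not exclude the first dose, which uses every draw and fits Aim 1's opening reference to comparing the two vaccines.

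A second reply is that same-week contrasts are proper randomised comparisons. This also stands. The Background says "we propose to compare the response to PPSV23 with a novel schedule of PCV13 followed by PPSV23 given eight weeks later", and Aim 1's second sentence sets out the same two schedules. For that question, time since PPSV23 is part of the schedule and not a confounder. A reader might infer that the week-16 and week-24 comparisons are invalid or that the design is biased. The documents do not support that: the mismatch matters only when such a contrast is read as a test of priming. Nor does Aim 1 call for a week-24 comparison of levels on the first-dose count.

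A third reply is that the protocol template does not require endpoints for minimal-risk research. The plan nevertheless sets two non-inferiority margins, and a margin needs a defined time point.

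**Conclusion.** The point holds as an undefined anchor with a specific consequence. If the first-dose count is followed, neither Aim 1 contrast tests the priming hypotheses, and the week-16 contrast has A eight weeks further from PPSV23 than B. That offset follows from the schedule alone.

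The size of any distortion does not. A reader might take the 1.41-fold shift or the 22% false non-inferiority rate as an estimate for this trial. Both need a 16-week half-life, for which the documents give no support, and the 22% also needs a true halving of the response in B. With half-lives of 52 weeks or more the shift is at most 1.11 and the false non-inferiority rate at most 5.6%, under the same assumed SD and arm sizes.

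The point should be fixed before data are seen. The data stay usable and the remedy is cheap. Matching on time since PPSV23 removes the offset, but B's titres will still include any antibody that PCV13 itself induced. The matched contrast therefore measures the total response after the sequence, not the PPSV23 increment alone.

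**What to change.** In Aim 1 and Data Analysis, for both the proportion and the GMR analyses, state that:

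- the contrasts testing the priming hypotheses are indexed to PPSV23: A week 8 vs B week 16 as the lead contrast, then A week 16 vs B week 24;
- Aim 2's change runs from 8 to 16 weeks after PPSV23 in each arm (A weeks 8 to 16, B weeks 16 to 24);
- same-study-week contrasts are secondary, as a comparison of vaccines at week 8 and of schedules at weeks 16 and 24;
- B's titres after PPSV23 include any antibody induced by PCV13;
- whether B's week-8 draw is taken before its PPSV23 dose, and which draw is B's baseline for the fold rise.

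Replace the 12-month time points in Data Analysis with scheduled draws.

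The cost is wording only: no added subjects, draws or visits. There are two downsides. The matched contrasts use later Group B visits, so the number sampled should be reported by arm and visit to show any differential loss. Group A's week-24 draw has no matched Group B draw and serves only the schedule comparison.
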